10.2 Internal pilot phase

During the 12-month internal pilot phase, we plan to open sites at a rate of 1-2 sites per month and recruit at least one participant for every two months that a site is open, equating to a total of at least 77 participants from 12 sites within the allocated 12 months. The progression criteria from the internal pilot phase to the main study are highlighted in Table 4 below.

Progression criteria	Red	Amber	Green
Recruitment rate (per	<0.2	>0.2 but <0.5	>0 5
site/per month)	NU.5	20.5 Dut 20.5	20.5
Number of centres opened	<9	9-11	12
The % return of EQ-5D-5L	~750/	75 70%	>900/
data at 4-months	<75%	75-75%	20070
Total number of	<50	50.77	>77
participants recruited	<50	50-77	211

Table 4: Progression criteria from the internal pilot phase to the main study.

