10.1 Sample size

For the HAMLET study, a total target sample size of 386 participants, to be recruited over a period of 36 months, will be required to achieve 90% statistical power. This target was derived from a minimum clinically important difference of the EQ-5D-5L among a variety of patients with multiple co-morbidities and of similar demographics to the amputation population of 0.074 (mean) or 0.081 (median) (32). Estimating a loss to follow up rate of 20% and assuming an EQ-5D-5L difference of 0.074 with an estimated standard deviation of 0.2 (33), we would need to randomise 183 participants to each arm of the study to have 90% power (2p = 0.05); therefore, requiring a total of 386 participants.

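### The pilot total of 77 does not follow from 12 sites at 0.5 participants per site-month, so the rate and total rows of Table 4 are miscalibrated against each other

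*Protocol*

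**What the plan says.** Section 10.2 gives an opening plan, "we plan to open sites at a rate of 1-2 sites per month". In the same sentence it commits the pilot to "recruit at least one participant for every two months that a site is open, equating to a total of at least 77 participants". That sets a minimum rate of 0.5 participants per site-month and presents the pilot total as its result. The sentence puts the number of sites at 12 and the period at 12 months.

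Table 4 then sets separate progression criteria. Three matter here:
- recruitment rate per site per month, with Green starting at 0.5;
- "Number of centres opened": Red below 9, Amber 9 to 11, Green at 12;
- total recruited: Red below 50, Amber 50 to 77, Green from about 77 upwards.

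Section 4.1 says that a report goes to the funder at the end of the pilot and that the main trial depends on the funder's approval.

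**The concern.** The sentence in 10.2 presents 77 as the consequence of the opening plan and the rate. If it is not, the rate row and the total row of Table 4 describe different pilots. A pilot that did what 10.2 plans could meet the rate and centre criteria and still fall short on total, even into Red. Section 3.2 makes robust estimates of recruitment and site set-up an objective of the pilot, and these criteria support the case for continuing. If the mismatch is found only once pilot data are in, someone must decide afterwards which row to trust. That weakens the purpose of setting criteria in advance.

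**Working it through.** **Inputs, all from section 10.2 and Table 4:** pilot length 12 months; one to two openings a month; 12 sites; 0.5 participants per site-month; stated total 77; Red on total below 50.

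**Formula.** Expected participants = total site-months × 0.5. The rate needed for 77 = 77 / site-months. The protocol does not say when in a month a site opens, so both extremes are shown.

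| Opening of 12 sites | Site-months | Participants at 0.5 | Rate needed for 77 |
|---|---|---|---|
| One a month, start of month | 12+11+…+1 = 78 | 39 | 77/78 = 0.99 |
| One a month, end of month | 11+10+…+0 = 66 | 33 | 77/66 = 1.17 |
| Two a month, start of month | 2×(12+11+10+9+8+7) = 114 | 57 | 77/114 = 0.68 |
| Two a month, end of month | 2×(11+10+9+8+7+6) = 102 | 51 | 77/102 = 0.75 |
| All 12 on day 1 (not the stated plan) | 12×12 = 144 | 72 | 77/144 = 0.53 |

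An intermediate pace of 1.5 a month gives 88 to 100 site-months, so 44 to 50 participants.

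**Can the stated 77 be reproduced?** Not with 12 sites; even the day-1 ceiling is 72. The one variant tried that reaches it is two sites a month, opened at the start of every month for the whole year. That is 2×78 = 156 site-months, or 78 participants, but from 24 sites. The sentence says 12, and Table 4 sets Green for centres at 12.

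**What Table 4 returns with 12 centres open (Green) and a rate of 0.5:**
- one site a month: 33 to 39, Red on total;
- two sites a month: 51 to 57, Amber on total;
- all 12 on day 1: 72, still Amber.

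**Does this depend on whether Green on rate means above 0.5 or at least 0.5?** No. At 0.6, which is Green either way, one site a month gives 66×0.6 = 39.6 to 78×0.6 = 46.8, still Red. Two a month gives 102×0.6 = 61.2 to 114×0.6 = 68.4, still Amber. At one site a month the total leaves Red only at a rate of 50/78 = 0.64 to 50/66 = 0.76.

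**The case against.** The strongest reply is that 0.5 is a floor and the Green rate band is open-ended. A pilot opening two sites a month and recruiting about 0.68 to 0.75 per site-month would meet every stated condition and reach 77. This stands: a reader might infer that 77 is out of reach, and the protocol does not support that. It does not rescue the sentence, which says that the floor rate itself equates to at least 77.

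Second, rate and total measure different things, so differing colours are not in themselves a defect. The protocol nowhere says that every row must be Green or that one Red row stops the trial, and the funder sees all the rows. This also stands. One cannot say that the decision to continue turns on a single row. What remains is that the two thresholds come from one sentence that treats them as equivalent, and they are not. Green against Red arises towards the slow end of the opening plan; at two sites a month it is Green against Amber.

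Third, a reader might carry 12 sites at 0.5 forward and conclude that 386 participants in 36 months is infeasible. The document does not support this. Sections 4.1, 8.0 and 14.0 expect further sites after the pilot, and 10.2 does not offer the pilot rate as proof that the full target is feasible.

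Finally, 77 is close to 20% of 386 (77.2), but the protocol does not say where the figure came from, so that origin is only a guess.

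**Conclusion.** The point holds as an arithmetic error with a limited consequence. The 77 exceeds what 10.2's own inputs give: it is roughly twice the yield at one site a month (77/39 = 2.0 to 77/33 = 2.3) and about 1.4 to 1.5 times the yield at two (77/57 to 77/51). A pilot exactly on plan at the floor rate with 12 centres open cannot score Green on total.

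The figures assume that every open site recruits at 0.5 on average from the day it opens and that exactly 12 sites open. The timing of openings within the month moves the results only within the ranges shown.

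The error affects the calibration of one progression criterion. It does not touch the trial's sample size, the primary analysis, safety or the treatment estimate. It should be fixed, but it does not threaten the validity of the trial.

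**What to change.** Before the pilot is judged, agree one of two changes with the funder:

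1. State an opening schedule for the 12 sites and recompute the total row from it at 0.5 per site-month, rescaling the Red and Amber bands as well as the Green threshold. Depending on the schedule, the expected total lies between about 33 and 57.
2. Keep 77 and raise the Green rate to what it implies under the stated schedule: about 0.68 to 0.75 per site-month at two sites a month, or 0.99 to 1.17 at one.

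In either case, correct the sentence in 10.2 so that sites, schedule, rate and total agree.

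The cost is a change of wording and of Table 4, with the funder's agreement, and no added participants or procedures. The downside is a pilot total that looks less favourable under the first option, or a stricter rate threshold under the second.

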10.3 Statistical analysis

All analyses will be described in detail in a statistical analysis plan (SAP) which will be finalised prior to the end of data collection and will be reviewed and approved by the TSC and DMC. The SAP will be made publicly available via the ISRCTN registry. Analyses will be carried out on a locked dataset and performed using two-sided statistical tests at 5% significance under the principles of intention-to-treat. All analyses will be conducted taking into consideration the reporting requirements of the Consolidated Standards of Reporting Trials (CONSORT).

The primary analysis will compare the EQ-5D-5L scores between groups using a covariance pattern mixed-effect linear regression model, incorporating all post randomisation time points.

Treatment group, time, treatment-by-time interaction, stratification factors and baseline covariates will be included as fixed effects. Participants will be included as a random effect accounting for repeated observations per patient. Estimates of the difference in EQ-5D-5L scores will be extracted for each time point (primary outcome at 24 months) and overall, with two sided 95% CIs. Three planned subgroup analyses will be performed by including the additional baseline variable, two- and three-way interactions between the subgroup, allocation and time point in the primary analysis: frailty; amputation aetiology and sex.

10.4 Health economic analysis

A within-trial cost-utility analysis (CUA) will be undertaken from an NHS and personal social services (PSS) perspective to assess the cost effectiveness of TKA compared to AKA in adult patients requiring MMLA but who are unsuitable for a BKA

Costs considered in this economic analysis will include intervention costs within hospitals and costs of post-surgery healthcare service use. Intervention costs will be calculated by quantifying hospital record data extracted after discharge and applying national average costs (34). Post-surgery service use costs will be calculated by collecting data using a bespoke patient self-report resource utilisation questionnaire and multiplying by unit costs obtained from national databases, such as the UK national database of National Cost Collection (34) and the Unit Costs of Health and Social Care report produced by the Personal Social Services Research Unit (35). The post-surgery service use will include residential care, primary care, hospital care, social services and wider societal costs, such as productivity and patient costs.

Effectiveness for the health economic analysis will be measured using EQ-5D-5L (13) administered at each follow up. The EQ-5D-5L results will be valued and mapped to 3L values using the approach recommended by NICE (36) to provide utility scores at multiple follow-up time points, while Quality Adjusted Life Years (QALYs) will be calculated using the area under the curve (AUC) method over the study period (37).

The primary outcome of the cost-utility analysis will be the incremental costeffectiveness ratio (ICER) to combine the estimated costs and QALYs. Rubin's multiple imputation method will be used to impute missing data (38); while regression methods will be used to control for differences in baseline utility (39) and other prognostic variables, following the approach recommended by Glick and colleagues (40). The regression coefficient on treatment will then represent the mean difference in cost and QALYs between TKA and AKA. To assess the uncertainty, a, a nonparametric bootstrap method with 5000 iterations will be used to produce confidence intervals around the cost and QALY differences. Results will be presented in the conventional form of cost-effectiveness acceptability curves (CEAC) (41) to show the probability of the intervention being cost-effective over a range of willingness-to-pay (WTP) thresholds.

A range of pre-specified sensitivity analyses will be conducted to test the robustness of the primary outcomes under different scenarios. This includes a cost-utility analysis using complete cases, defined as patients who had both complete cost and EQ-5D-5L data at all follow-up time points, to access the impact of missingness and a cost-utility analysis from a societal perspective to explore the impact of wider costs, such as private expenses and productivity costs.

A detailed *a priori* health economics analysis plan will be developed to maintain the integrity and neutrality of the heath economic evaluation.

10.5 Qualitative analysis

Analysis of the interviews conducted during the pilot study will focus on exploring patient views of the trial and how the interventions were described, to inform

changes to recruitment materials; this will be fed back to recruiting staff. Semistructured longitudinal interviews with trial participants will capture longer-term recovery and will focus on understanding the trade-offs made to allow trial participants to adapt to their new circumstances, the impact of multi-morbidity, and perceived functionality of their amputation level. Towards the end of the recruitment period, semi-structured interviews with ~20 clinicians from across sites will explore implementation issues. Data from trial participant interviews / site staff interviews will provide insight into the perceived factors influencing intervention adoption at sites. Data analysis will be undertaken in parallel with data collection so analysis of early interviews can inform later sampling decisions and interview questions.

Transcription of all interview data will be undertaken by a company contracted to the University of Hull under an existing confidentiality agreement. All data will be sent to the transcription company via secure upload links. Transcripts will be anonymised at point of transcription, and checked manually when received by the research team before analysis begins. NVivo qualitative data analysis software will be used to store and manage the transcripts during analysis. Field notes taken after each interview will be used to support the analysis.

For patient interviews, inductive thematic data analysis will be undertaken with transcripts coded by ascribing words and phrases to capture the meaning in the text to identify common emerging ideas. Staff interviews will be coded using a deductive and inductive approach with Normalisation Process theory used to guide the analysis (42).

To ensure reliability in the coding a subset of transcripts will be dual coded by two experienced qualitative researchers and any discrepancies discussed with the core research team until consensus reached. A coding index will be developed using the first five transcripts and applied to the remaining transcripts by one researcher. Regular qualitative team meetings (qualitative lead, PPI, and Chief investigator) will be used to discuss the possible themes identified in the data, and to ensure the analysis remains grounded in the data. PPI input will inform the interpretation of the

key findings. The Pillar integration process (43) will be used as a framework to integrate the quantitative trial data and qualitative findings.

10.6 SWAT analysis

The protocols for each are available on the MRC SWAT repository (recruitment: SWAT 15 (26), retention: SWAT 180 (27).

10.6.1 Recruitment SWAT

An 'intention-to-treat' analysis will be performed including all randomised sites analysed in the SWAT group to which they were allocated.

Both demographic characteristics, including age, sex, and ethnic group of randomised participants and site characteristics, including geographical location and catchment size, will be presented descriptively as mean (standard deviation) or number (%), as appropriate.

The primary analysis will compare the difference in recruitment rates between those receiving the animation in addition to the PIL and those not receiving the animation. This outcome will be analysed using mixed effect logistic regression with a fixed effect for SWAT allocation and a random intercept for site.

Secondary analysis: The difference in the proportion of those responding to a recruitment invitation who received the animation in addition to the PIL but who do not go on to be randomised, and those not receiving the animation but who do not go on to be randomised will also be analysed using a similar model to the primary outcome.

The difference in cost per recruited participant between those offered the animation and those not offered the animation will be calculated. In addition to the direct costs of the animation, it may also be necessary to include the cost of staff time spent administering the recruitment packs.

The following sensitivity analyses will be performed for the primary analysis:

• Excluding participants who did/could not receive allocation as randomised.

Subgroup analysis may also be performed for key demographic subgroups (e.g. age, gender, ethnicity) by adding interaction terms to the logistic regression or Cox regression model, where the sample size is deemed sufficiently large.

Where available, a meta-analysis, including data from existing SWATs will be undertaken to incorporate the results from this SWAT.

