4.5 Studies Within a Trial (SWAT)

The HAMLET study will act as a host trial for two individual Studies Within a Trial (SWAT), designed to evaluate the effectiveness of either a participant recruitment or retention strategy. The protocols for each are available on the MRC SWAT repository (recruitment: SWAT 15 (26), retention: SWAT 180 (27)). As is usual with embedded trials, the sample size will be informed by the number of participants approached to participate in the main study (for the recruitment SWAT) or those participating in the study (for the retention SWAT).

4.5.1 Recruitment SWAT: The effectiveness of a study explanatory animation We will evaluate the effects of mode of presentation of the study design to participants on recruitment rate. Participants will be randomised (on a site basis) to receive an animated explanatory video (explaining the study) plus the standard patient information sheet (PIS) or just the PIS.

Successful clinical trial recruitment is an ongoing challenge, with a recent review estimating that 37% of trials fail to meet their recruitment targets (28). The PRioRiTy study of recruitment research prioritised "what are the best approaches

for designing and delivering information?" to potential participants as the fourth most important unanswered issue (29).

A review of recruitment strategies identified 35 studies focusing on information delivery, but almost all were low or very low methodological quality (30). Only three studies evaluated use of video information provision, with very low-GRADE certainty evidence. At the time of the review, no studies evaluated animations as a method of providing study information. The popularity of animations is however increasing and hence evaluation is required.

As is usual with embedded trials, the sample size is constrained by the number of patients approached about the study hence a formal power calculation to determine sample size has not been conducted.

This will be a cluster trial; randomisation will be carried out at the site level to reduce cross contamination. The allocation ratio will be 1 to 1. Generation of the allocation sequence will be undertaken independently by a researcher not involved with the recruitment of participants.

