The primary outcome of this embedded trial will be the recruitment rate, i.e. the proportion of participants in each group who are randomised into the host trial. Secondary outcomes will include the proportion of patients in each group who are screened but do not go on to be randomised, and the cost effectiveness of the intervention.

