6.0 Trial processes

6.1 Participant identification

The study management team at York Trials Unit (YTU) will work closely with surgeons, clinicians and research teams at each study site to optimise the screening and recruitment process for local circumstances. Participating sites will retain screening logs to capture the number of ineligible and non-consenting patients, which will be transferred to YTU on a regular basis. For all patients who require a MLLA and are not suitable for a BKA, we will record whether the patient has been approached and/or consented to take part in the trial. If the patient has not been recruited into the trial, the reason for this will be recorded (e.g. ineligible, not approached, not consented). The trial team will use this information, alongside the qualitative investigations during the pilot phase, to identify potential areas where recruitment processes require improvement.

The screening process will be consistent for all patients undergoing a MLLA and will be performed by the treating clinician or research team in the ward or clinic when the decision to proceed to MLLA is made. Once a patient has been screened against the study eligibility criteria and deemed suitable for inclusion, they will be approached for study participation.

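### The recruitment SWAT's secondary outcome is defined among screened patients but analysed among responders to an invitation, a step the protocol does not describe and the animation could change

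*Protocol*

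**What the plan says.** Protocol section 4.5.1 sets the recruitment SWAT up as a cluster trial: "randomisation will be carried out at the site level to reduce cross contamination. The allocation ratio will be 1 to 1". Its primary outcome is "the recruitment rate, i.e. the proportion of participants in each group who are randomised into the host trial"; the population over which that proportion is taken is not named. One secondary outcome is "the proportion of patients in each group who are screened but do not go on to be randomised". There is no power calculation, because "the sample size is constrained by the number of patients approached about the study".

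Section 10.6.1 commits to intention-to-treat by allocated site and fits, for the primary outcome, "mixed effect logistic regression with a fixed effect for SWAT allocation and a random intercept for site". For the secondary outcome it uses a similar model but another population: "The difference in the proportion of those responding to a recruitment invitation who received the animation in addition to the PIL" and were not then randomised, against the corresponding patients without the animation.

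Section 6.1 fixes the order of events: "Once a patient has been screened against the study eligibility criteria and deemed suitable for inclusion, they will be approached for study participation". It also says what is logged: "Participating sites will retain screening logs to capture the number of ineligible and non-consenting patients". Section 6.2 goes on to the information sheet, the animation where applicable, time to decide, and written consent. Neither section describes a step in which a patient responds to an invitation.

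**The concern.** One outcome has two denominators. This is more than detail left for an analysis plan, because the protocol states a population twice and the two do not agree.

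Each denominator also has its own difficulty. Screening comes before approach, so screened patients include people found ineligible, who are never given the information sheet or the animation. They add non-randomised patients to both arms whatever the animation does. Responders, if they could be identified, would be selected after site allocation by something the animation is meant to influence. Comparing arms within that group is no longer the comparison that randomising sites protects.

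At stake is whether this secondary result can be read as an effect of the animation at all.

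**Working it through.** **Figures in the plan.** The SWAT states no sample size, effect or rate, so there is nothing to reproduce. The check sets the sections side by side and adds illustrative arithmetic with assumed rates.

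**The candidate populations**

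| Population | Where it appears | Who is in it |
|---|---|---|
| Screened | 4.5.1, definition of the secondary outcome | Includes ineligible patients who see neither sheet nor animation (6.1) |
| Responders to an invitation | 10.6.1, analysis of the same outcome | No such step in 6.1 or 6.2; would arise after allocation |
| Approached | 4.5.1, only as the reason for no power calculation | Patients found suitable at screening (6.1) |

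**Assumed inputs.** Among approached patients, p0 = 40% are randomised with the information sheet alone and p1 = 50% with the animation. The difference is 10 points, the odds ratio (0.50/0.50)/(0.40/0.60) = 1.50 and the risk ratio for being randomised 0.50/0.40 = 1.25. Results below are for being randomised. For not being randomised, each difference changes sign and each odds ratio inverts.

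**Screened denominator.** Let s be the share of screened patients who are approached, equal in both arms. Then P(randomised | screened) = s × P(randomised | approached), and the difference is s × 10 points.

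| s | Sheet alone | Animation | Difference | Odds ratio | Risk ratio, randomised | Risk ratio, not randomised |
|---|---|---|---|---|---|---|
| 1.0 | 40% | 50% | 10 points | 1.50 | 1.25 | 0.83 |
| 0.8 | 32% | 40% | 8 points | 1.42 | 1.25 | 0.88 |
| 0.6 | 24% | 30% | 6 points | 1.36 | 1.25 | 0.92 |
| 0.4 | 16% | 20% | 4 points | 1.31 | 1.25 | 0.95 |
| 0.2 | 8% | 10% | 2 points | 1.28 | 1.25 | 0.98 |

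The difference and odds ratio are diluted. The risk ratio for being randomised is not, because s cancels. The secondary outcome, however, is framed as *not* being randomised, and that risk ratio does move towards 1.

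**Responder denominator.** Let r0 and r1 be the response rates among approached patients, and suppose everyone randomised has responded. Then P(randomised | responded) = p/r, and the risk ratio among responders is (p1/p0) × (r0/r1) = 1.25 × r0/r1.

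| r0 | r1 | Sheet alone | Animation | Difference | Odds ratio | Risk ratio |
|---|---|---|---|---|---|---|
| 80% | 70% | 50.0% | 71.4% | +21.4 points | 2.50 | 1.43 |
| 60% | 60% | 66.7% | 83.3% | +16.7 points | 2.50 | 1.25 |
| 60% | 70% | 66.7% | 71.4% | +4.8 points | 1.25 | 1.07 |
| 60% | 75% | 66.7% | 66.7% | 0 points | 1.00 | 1.00 |
| 60% | 80% | 66.7% | 62.5% | -4.2 points | 0.83 | 0.94 |

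With equal response (second row) the larger difference is a change of scale, and the risk ratio stays at 1.25. Once response differs between arms, the risk ratio itself is inflated, removed or reversed. Reversal needs r1/r0 to exceed p1/p0.

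**Approached denominator.** Every approached patient is either randomised or not, so the secondary outcome is exactly one minus the recruitment rate. It then carries no information beyond the primary outcome.

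**The case against.** The strongest reply is that this is loose wording in one secondary outcome of an embedded study that was never powered, and that several larger complaints do not follow from it. Much of that stands.

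- A reader might infer that the SWAT counts patients in three populations. It does not: approached patients appear only to explain the absent power calculation. The conflict is between two denominators for one secondary outcome. The primary outcome leaves its denominator unnamed but uses neither of them.
- A reader might infer from the receipt wording that intention-to-treat is abandoned. Section 10.6.1 states analysis by allocated site and fits a term for allocation. It also lists, as a sensitivity analysis of the primary comparison, excluding those who did not get their allocation, which presupposes that the main analysis keeps them. The wording should be tidied, but the rule is clear.
- A reader might conclude that the animation will look harmful. Reversal needs it to raise response proportionally more than recruitment, and nothing in the protocol supports any particular pair of rates.
- A reader might expect damage to the planned meta-analysis. Section 10.6.1 does not say that the secondary outcome will be pooled.
- It would go too far to say that every approach is made in person. Section 6.1 places screening on the ward or in clinic but does not say how the approach is made, and section 10.6.1 mentions recruitment packs. What can be said is that no response step is defined.
- The cited repository protocol for this SWAT may be clearer, but the disagreement lies within this document.

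The reply does not remove the main point. Following section 10.6.1 as written means selecting patients on something that happens after allocation and that the animation could change.

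**Conclusion.** The point holds in a limited form. The secondary outcome is defined on one population and analysed on another. The responder condition is unsound as an analysis rule, and the screened denominator dilutes the difference and odds ratio. The risk ratio for recruitment escapes dilution only if the eligible (approached) share is the same in both arms.

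The direction of these effects follows from the structure of the design. Their size cannot be fixed from the protocol: every rate in the working is an assumption, and inflation, no effect and reversal all lie within the range shown. The finding calls for a wording correction. It does not affect the host trial or its EQ-5D-5L analysis.

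**What to change.** 1. In section 10.6.1, delete the condition on responding to an invitation, and describe the groups as patients at sites allocated, or not allocated, to the animation instead of those who received it.
2. State one denominator, fixed before any response, in both 4.5.1 and 10.6.1. One workable choice is patients found eligible at screening and approached, taken from the section 6.1 logs. Eligibility should be as judged at screening, because the willingness criterion in section 5.1 may be known only after approach.
3. Report by arm the numbers screened and the numbers eligible but not approached, so that any differential approach is visible.
4. Since the secondary outcome then equals one minus the recruitment rate, drop it, or replace it with the reason for non-randomisation, such as approached and declined.

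The cost is protocol wording. Section 6.1 already has sites record, for each patient needing amputation who is unsuitable for below-knee surgery, whether they were approached or consented and why they were not recruited. The small downside is that approach is in the hands of site staff who know their site's allocation, which is why the by-arm counts in step 3 are needed. Using all eligible logged patients would avoid that, but would bring back people who were never approached and never saw the animation.
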